### 3.1.1.1 Cobimetinib and Atezolizumab Treatment Schedule

Cobimetinib will be administered orally at a starting dose of 60 mg QD starting on Day 1 through Day 21 followed by a 7-day rest of each 28-day cycle in all cohorts.

Atezolizumab will be administered by IV infusion at a fixed dose of 840 mg on Days 1 and 15 of each 28-day cycle. Patients in the biopsy cohort (Cohort 7) will begin dosing cobimetinib before atezolizumab and will receive 60 mg cobimetinib alone QD, starting on Day 1 through Day 14 for Cycle 1. Atezolizumab dosing (840 mg IV) will begin on Day 15 in Cycle 1 and will continue on Days 1 and 15 of every cycle thereafter. Both study drugs will be administered until unacceptable toxicity or loss of clinical benefit, as determined by the investigator, after an integrated assessment of radiographic and biochemical data, and clinical status (e.g., symptomatic deterioration such as pain secondary to disease). If one study drug is discontinued or temporarily withheld or dose reduced, the other study drug may be continued.

Because of the possibility of an initial increase in tumor burden caused by IC infiltration in the setting of a T-cell response (termed "pseudoprogression") with atezolizumab containing treatment, radiographic progression per RECIST v1.1 may not be indicative of true disease progression. In the absence of unacceptable toxicity, patients who meet criteria for disease progression per RECIST v1.1 while receiving cobimetinib and/or atezolizumab will be permitted to continue study treatment if they meet all of the following criteria:

- Evidence of clinical benefit, as determined by the investigator following a review of all available data
- Absence of symptoms and signs (including laboratory values, such as new or worsening hypercalcemia) indicating unequivocal progression of disease
- Absence of decline in Eastern Cooperative Oncology Group (ECOG) Performance Status that can be attributed to disease progression

- Absence of tumor progression at critical anatomical sites (e.g., leptomeningeal disease) that cannot be managed by protocol-allowed medical interventions
- Patient's written consent to acknowledge deferring other treatment options in favor of continuing study treatment at the time of initial disease progression

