**Table 5 Guidelines for Management of Patients Who Experience Specific Adverse Events (Cobimetinib and Atezolizumab)**

Event	Action to Be Taken
General guidance for dose modifications and treatment delays and discontinuation	
 
• There will be no dose modifications for atezolizumab.
 
• If atezolizumab is withheld and corticosteroids are initiated for an atezolizumab-related toxicity, corticosteroids must be tapered over <math>\geq 1</math> month to <math>\leq 10</math> mg/day oral prednisone or equivalent before atezolizumab can be resumed.a, b The dose of cobimetinib can be reduced by 20 mg (1 dose level) up to 2 times (i.e., from 60 mg to 40 mg and then from 40 mg to 20 mg). If further dose reduction is indicated after two dose reductions, the patient must discontinue cobimetinib but may continue treatment with atezolizumab at the investigator's discretion.
 
• If atezolizumab is discontinued, treatment with cobimetinib may be continued at the investigator's discretion and after discussion with the Medical Monitor.
 
• If cobimetinib is withheld for <math>> 28</math> days because of toxicity, the patient should be discontinued from cobimetinib, unless resumption of treatment is approved by the Medical Monitor after discussion with the investigator.
 

IRRs, anaphylaxis, and hypersensitivity reaction	
 
• Guidelines for management of IRRs are provided in Appendix 8.
 
• For anaphylaxis precautions, see Appendix 7.
 
• For severe hypersensitivity reactions, permanently discontinue all study treatment.
 

IRR = infusion-related reaction.

a Atezolizumab may be withheld for a period of time beyond 12 weeks to allow for corticosteroids to be reduced to  $\leq 10$  mg/day oral prednisone or equivalent. The acceptable length of the extended period of time must be agreed upon by the investigator and the Medical Monitor.

b Resumption of atezolizumab may be considered in patients who are deriving benefit and have fully recovered from the immune-related event. Patients can be rechallenged with atezolizumab only after approval has been documented by both the investigator (or an appropriate delegate) and the Medical Monitor.

**Table 5 Guidelines for Management of Patients Who Experience Specific Adverse Events (Cobimetinib and Atezolizumab) (cont.)**

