a Grade 1: Asymptomatic or mild symptoms; clinical or diagnostic observations only; intervention not indicated.

b Grade 2: Moderate; minimal, local or noninvasive intervention indicated; limiting age appropriate instrumental ADL.

c Grade 3: Severe or medically significant but not immediately sight threatening; hospitalization or prolongation of existing hospitalization indicated; disabling; limiting self-care ADL.

d Grade 4: Sight-threatening consequences; urgent intervention indicated; blindness (20/200 or worse) in the affected eye.

**Table 5 Guidelines for Management of Patients Who Experience Specific Adverse Events (Cobimetinib and Atezolizumab) (cont.)**

Event	Action to Be Taken
Ocular toxicity (cont.)	
Potential immune-related ocular toxicity (e.g., uveitis, iritis, episcleritis, or retinitis)	
 
• Follow guidelines provided in Appendix 8.
 
• Continue cobimetinib as clinically indicated.
 

RVO (any grade)	
 
• If RVO (any grade) is diagnosed, cobimetinib dosing should be permanently discontinued and RVO treated per institutional guidelines.
 
• Continue atezolizumab.
 

RVO = retinal vein occlusion.

**Table 5 Guidelines for Management of Patients Who Experience Specific Adverse Events (Cobimetinib and Atezolizumab) (cont.)**

LVEF Decrease from Baseline				
Patient	LVEF Value	Recommended Action with Cobimetinib and Atezolizumab	LVEF Value following Treatment Break	Recommended Cobimetinib Daily Dose
Asymptomatic	≥ 50% (or 40%–49% and < 10% absolute decrease from baseline)	Continue atezolizumab and cobimetinib at current dose.	NA	NA
	< 40% (or 40%–49% and ≥ 10% absolute decrease from baseline)	Interrupt cobimetinib treatment for 2 weeks. Continue atezolizumab as clinically indicated.	< 10% absolute decrease from baseline	First occurrence: 40 mg
				Second occurrence: 20 mg
				Third occurrence: permanent discontinuation
< 40% (or ≥ 10% absolute decrease from baseline)	Permanent discontinuation			
Symptomatic	NA	Interrupt cobimetinib treatment for 4 weeks. Consider withholding atezolizumab. Discuss with Medical Monitor regarding resumption of atezolizumab. Cardiology consultation is strongly recommended.	Asymptomatic and < 10% absolute decrease from baseline	First occurrence: 40 mg
				Second occurrence: 20 mg

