				Third occurrence: permanent discontinuation
			Asymptomatic and < 40% (or ≥ 10% absolute decrease from baseline)	Permanent discontinuation
Symptomatic regardless of LVEF	Permanent discontinuation			

LVEF = left ventricular ejection fraction; NA = not applicable.

**Table 5 Guidelines for Management of Patients Who Experience Specific Adverse Events (Cobimetinib and Atezolizumab) (cont.)**

Event	Action to Be Taken
Rhabdomyolysis or CPK elevation	
General guidance	
 
• Rule out cardiac cause (check ECG, serum cardiac troponin, and CPK-isoforms M and B fraction) and rule out rhabdomyolysis (clinical examination; serum creatinine, potassium, calcium, phosphorus, uric acid, and albumin; and urine myoglobin).
 
• Assess patient for any history of strenuous physical activity, blunt trauma, or recent intramuscular injections.
 

For Grade $\leq 3$ CPK elevations that are asymptomatic and deemed not clinically significant	
 
• Cobimetinib and atezolizumab dosing does not need to be modified or interrupted to manage asymptomatic Grade <math>\leq 3</math> CPK elevations.
 
• Recheck CPK at least once a week.
 

For Grade 4 CPK elevations that are asymptomatic and deemed not clinically significant	
 
• Interrupt cobimetinib and atezolizumab treatment.
 
• If improved to Grade <math>\leq 3</math> within 4 weeks, restart cobimetinib at a dose reduced by 20 mg, if clinically indicated.
 
• If CPK elevations do not improve to Grade <math>\leq 3</math> within 4 weeks following dose interruption, permanently discontinue cobimetinib treatment.
 
• Resumption of atezolizumab may be considered in patients who are deriving benefit.
 

Rhabdomyolysis or symptomatic CPK elevations	
 
• Interrupt cobimetinib and atezolizumab treatment.
 
• If severity is improved by at least one grade and symptoms resolve within 4 weeks, restart cobimetinib at a dose reduced by 20 mg, if clinically indicated.
 
• If rhabdomyolysis or symptomatic CPK elevations do not improve within 4 weeks, permanently discontinue cobimetinib treatment
 
• Resumption of atezolizumab may be considered in patients who are deriving benefit after discussion with the Medical Monitor.
 

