**Table 5 Guidelines for Management of Patients Who Experience Specific Adverse Events (Cobimetinib and Atezolizumab) (cont.)**

Event	Action to Be Taken
Hemorrhage	
Grade 3 hemorrhage	
 
• Interrupt cobimetinib treatment. There are no data on the effectiveness of cobimetinib dose modification for hemorrhage events. Clinical judgment should be applied when considering restarting cobimetinib treatment.
 
• Continue atezolizumab treatment.
 

Grade 4 hemorrhage or any grade cerebral hemorrhage	
 
• Interrupt cobimetinib treatment. Permanently discontinue cobimetinib for hemorrhage events attributed to cobimetinib.
 
• Continue atezolizumab treatment.
 

Grade 3 or 4 or intolerable Grade 2 treatment-related toxicities not described above and in Table 4 (dose modifications for cobimetinib)	
 
• Withhold all study treatment.
 
• If event resolves to Grade 1 or better within 12 weeks, resume atezolizumab at fixed dose. If not, permanently discontinue atezolizumab. a, b, c
 
• If event resolves to Grade 1 or better within 28 days, resume cobimetinib with dose reduced by one level. If not, permanently discontinue cobimetinib.
 

a If corticosteroids have been initiated, they must be tapered over  $\geq 1$  month to  $\leq 10$  mg/day oral prednisone or equivalent before atezolizumab can be resumed.

b Atezolizumab may be withheld for a period of time beyond 12 weeks to allow for corticosteroids to be reduced to  $\leq 10$  mg/day oral prednisone or equivalent. The acceptable length of the extended period of time must be agreed upon by the investigator and the Medical Monitor.

c Resumption of atezolizumab may be considered in patients who are deriving benefit and have fully recovered from the immune-related event. Patients can be rechallenged with atezolizumab only after approval has been documented by both the investigator (or an appropriate delegate) and the Medical Monitor.

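### Table 5 sets the cobimetinib restart dose after an LVEF fall by event number alone, so a patient already on 40 mg restarts with no reduction

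*Combined protocol and SAP*

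**What the plan says.** Section 3.1.1.1 sets the starting point: "Cobimetinib will be administered orally at a starting dose of 60 mg QD".

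The LVEF block of Table 5 (Section 5.1.3.4) has an asymptomatic part and a symptomatic part. Each requires cobimetinib to be interrupted, for 2 weeks if asymptomatic and 4 weeks if symptomatic. If LVEF recovers to less than 10% absolute below baseline, each gives the same ladder in a column of recommended daily doses: "First occurrence: 40 mg", "Second occurrence: 20 mg", "Third occurrence: permanent discontinuation". Only the row for patients below the action threshold mentions the dose being taken: "Continue atezolizumab and cobimetinib at current dose".

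The general guidance at the top of Table 5 says "The dose of cobimetinib can be reduced by 20 mg (1 dose level) up to 2 times", spelled out as 60 to 40 mg and then 40 to 20 mg. It adds: "If further dose reduction is indicated after two dose reductions, the patient must discontinue cobimetinib". Table 4 (Section 5.1.3.1) prints the same 40 mg and 20 mg by first and second appearance. Its note allows re-escalation case by case after discussion with the Medical Monitor.

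**The concern.** The printed doses are reductions throughout only if the patient is on 60 mg at the first LVEF event, and the block does not state that assumption. Cobimetinib is reduced for many other toxicities, so a patient can reach a first LVEF event already on 40 mg. Read literally, the row then returns that patient to the MEK-inhibitor dose at which LVEF fell.

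Section 5.1.1.1.3 lists left ventricular dysfunction as an important identified risk of cobimetinib. In the Phase III cobimetinib plus vemurafenib study, Grade 2 or 3 decreased LVEF occurred in 8.5% against 3.7% with placebo plus vemurafenib. The same section credits the dose modification guidelines with managing most of these events.

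There is a second effect. Section 4.5.8 gives extra LVEF checks at about 2, 4, 10 and 16 weeks to patients who restart at a reduced dose because of LVEF. A restart from 40 mg to 40 mg is not a reduction, so on a literal reading those checks are not triggered either.

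**Working it through.** No sample size or power figure is involved. The check treats the LVEF block as a mapping from LVEF event number and dose at onset to restart dose, and compares it with a rule that always steps down.

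**Inputs.** Starting dose 60 mg (Section 3.1.1.1). Printed restart dose P = 40 mg at the first event and 20 mg at the second (Table 5, LVEF block). One dose level = 20 mg (Table 5, general guidance). D = dose at onset of the LVEF event.

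**Comparison rule.** Restart at min(P, D - 20); discontinue if D = 20.

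| LVEF event | D (mg) | Printed P (mg) | P - D (mg) | Rule | Agree? |
|---|---|---|---|---|---|
| First | 60 | 40 | -20 | min(40, 40) = 40 | Yes |
| First | 40 | 40 | 0 | min(40, 20) = 20 | No |
| First | 20 | 40 | +20 | Discontinue | No |
| Second | 60 (after re-escalation) | 20 | -40 | min(20, 40) = 20 | Yes |
| Second | 40 | 20 | -20 | min(20, 20) = 20 | Yes |
| Second | 20 | 20 | 0 | Discontinue | No |

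At the third event both say discontinue. The two differ in 3 of 6 states.

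**Does other text correct the first event on 40 mg?** The printed change is 0%; the rule gives (20 - 40)/40 = -50%.

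- The Table 5 general guidance permits and caps reductions. It does not require one at an LVEF restart.
- Table 4 also prints 40 mg at first appearance. It would give 20 mg only if appearances are counted across toxicities, which it does not say.
- The catch-all row, which does require a one-level reduction, covers "Grade 3 or 4 or intolerable Grade 2 treatment-related toxicities not described above and in" Table 4. LVEF events have their own block above it, so it does not reach them.
- Section 4.5.8 presumes a reduction but is a monitoring instruction and sets no dose.
- The other Table 5 rows that direct a lower-dose restart (diarrhea, colitis, Grade 3 dermatologic events, raised AST/ALT with raised bilirubin, serous retinopathy, CPK elevation or rhabdomyolysis, and the catch-all) all word it relative to the current dose, as one level or 20 mg lower.

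This state is therefore open.

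**The two states at 20 mg.** A patient on 20 mg has used both reductions, so the general guidance requires discontinuation if a further one is indicated. Moving from 20 to 40 mg would also be a re-escalation, which the Table 4 note allows only after discussion with the Medical Monitor. A site applying those texts would not double the dose, but it would have to set the printed row aside.

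**Can the open state occur?** Yes. Grade 3 diarrhea leads to a one-level reduction: 60 - 20 = 40 mg. In the Phase Ib combination study (Section 1.2.6.2), Grade 3 or higher diarrhea was 8.0% of 150 patients, or 0.080 × 150 = 12. This shows the route only. It includes any Grade 4 cases and is neither a dose-reduction rate nor a count of patients affected.

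**The case against.** The strongest reply is that the protocol already has a single shared ladder: 60 to 40, 40 to 20, then stop. The general guidance stands over all of Table 5, the LVEF doses sit on the same ladder, and from 40 mg its only downward step is 20 mg. Section 4.5.8 describes LVEF restarts as reductions, and Table 4 can be read as counting appearances across toxicities. On that view, only an isolated reading of one cell gives 40 to 40 mg.

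This shows what was intended. It does not change the cell, which is the specific instruction for the event and names a dose.

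The remaining points stand as limits on size:

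- Only one of the three differing states is truly open.
- No count of affected patients can be given.
- The column is a recommendation, so a lower dose is not forbidden.
- Restart requires an interruption and LVEF recovery. Patients who do not recover stop permanently, and cardiology consultation is strongly recommended for symptomatic cases.
- A reduced restart is not universal in Table 5. Grade 2 pneumonitis resumes cobimetinib with no stated reduction, and the CPK reductions apply only if clinically indicated.

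None of these supplies the missing lower dose.

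**Conclusion.** The concern holds. As printed, a first LVEF event in a patient already on 40 mg for another toxicity leads to a restart at 40 mg, against the intent visible in Section 4.5.8 and out of line with the other reduced-dose restart rows. The two states at 20 mg are a lesser inconsistency, because the general guidance already overrides them.

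The conclusion rests on reading the LVEF rows as written and on Table 4 not stating that appearances are pooled across toxicities. The number of patients affected is small and cannot be estimated from the documents. No endpoint or planned analysis changes. It should be fixed because it is a safety-relevant dosing instruction that is cheap to correct.

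**What to change.** In both LVEF parts of Table 5, replace the fixed doses with:

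> Restart at the lower of (a) the dose for that LVEF occurrence (first 40 mg, second 20 mg) and (b) one dose level (20 mg) below the dose at event onset. Permanently discontinue if already at 20 mg at event onset, or at the third occurrence.

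This leaves the usual case (first event on 60 mg) unchanged. It also keeps the printed doses as an LVEF-specific ceiling for a patient who has been re-escalated: a second event on 60 mg still restarts at 20 mg, where a plain one-level rule would give 40 mg.

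The cost is a one-line wording change in the two LVEF rows at the next amendment and a clarification letter to sites. It needs no extra patients, visits or procedures.

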#### **4.1.2.2 Exclusion Criteria based on Organ Function or Medical History Cardiovascular**

Patients who meet the following cardiovascular exclusion criterion will be excluded from study entry:

- Left ventricular ejection fraction (LVEF) below the institutional lower limit of normal or <50%, whichever is lower

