#### **4.5.8 Left Ventricular Ejection Fraction**

For patients receiving cobimetinib, evaluations of LVEF are required.

Evaluation of LVEF by ECHO or MUGA scan must be performed at the following timepoints:

- Screening
- Day 1 of Cycle 2 ( $\pm 1$  week)
- At least every 3 months or as clinically indicated
- Treatment discontinuation visit

The treatment discontinuation visit evaluation of LVEF does not need to be performed at the treatment discontinuation visit if an evaluation has been performed within the last 12 weeks and there are no clinically significant findings and/or changes from baseline.

- After restarting treatment with a dose reduction of cobimetinib  
All patients restarting treatment with a dose reduction of cobimetinib because of a decrease in LVEF should have LVEF measurements taken after approximately 2 weeks, 4 weeks, 10 weeks, and 16 weeks, and then resume monitoring of LVEF every three treatment cycles.

Any patient who develops clinical signs or symptoms suspicious of cardiac failure should undergo an LVEF assessment. Evaluation of LVEF must be performed using the same method (ECHO or MUGA scan) for each patient. It is strongly encouraged that the same laboratory and operator perform each ECHO or MUGA scan for each individual patient. Investigators must be aware of local institution regulations regarding repeat MUGA scans.

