#### **5.1.1.1.3 Left Ventricular Dysfunction**

Decreases in LVEF from baseline have been reported in patients receiving cobimetinib. Left ventricular dysfunction may occur with signs and symptoms of cardiac failure, or reduction in LVEF may be asymptomatic.

Left ventricular dysfunction has been characterized in Study GO28141. The study incorporated prospective serial LVEF evaluations in all patients. With active surveillance, measured reductions in LVEF were observed more frequently in patients treated with cobimetinib plus vemurafenib than placebo plus vemurafenib (8.5% vs. 3.7%, respectively, of Grade 2 or 3 decreased LVEF). Of the patients treated with cobimetinib plus vemurafenib, 2 patients (0.8%) had symptomatic reduction in LVEF and the remaining patients were asymptomatic. Most LVEF reduction events in patients treated with cobimetinib plus vemurafenib improved or resolved with management according to dose modification guidelines (see Section 5.1.3).

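### Table 5's post-break LVEF rows overlap: below 40% with a fall under 10 points, one row restarts cobimetinib and the other stops it

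*Combined protocol and SAP*

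**What the plan says.** Table 5 manages LVEF decreases in two stages.

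**On treatment, asymptomatic patients.** Both drugs continue at LVEF "≥ 50% (or 40%–49% and < 10% absolute decrease from baseline"). Cobimetinib is interrupted for 2 weeks at LVEF "< 40% (or 40%–49% and ≥ 10% absolute decrease from baseline"). Symptomatic patients have cobimetinib interrupted for 4 weeks whatever the LVEF.

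**After the break, asymptomatic block.**
- Restart row: "< 10% absolute decrease from baseline". Dose 40 mg at the first occurrence, 20 mg at the second, permanent discontinuation at the third.
- Stop row: "< 40% (or ≥ 10% absolute decrease from baseline"). Permanent discontinuation.

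**After the break, symptomatic block.** The same pair appears for patients whose symptoms have resolved. The restart row again asks only for a fall of less than 10 points; the stop row reads "Asymptomatic and < 40% (or ≥ 10% absolute decrease from baseline"). Patients who are still symptomatic stop.

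**Entry.** Section 4.1.2.2, and the synopsis in the same terms, excludes "Left ventricular ejection fraction (LVEF) below the institutional lower limit of normal or <50%, whichever is lower". Section 9.2 does not allow eligibility waivers.

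**Follow-up.** Under Section 4.5.8, patients who restart at a reduced dose because of an LVEF decrease "should have LVEF measurements taken after approximately 2 weeks, 4 weeks, 10 weeks, and 16 weeks".

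**The concern.** The restart row tests only the change from baseline. The stop row tests either the change or the absolute value. The two are therefore not complements: a patient can pass the change test while LVEF is still below 40%. For that patient one row gives cobimetinib back at a reduced dose and the other withdraws it for good.

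This looks like an omitted condition, not a choice. The on-treatment rows carry the 40% floor on both sides of the decision. A patient restarted at 39% would already meet the on-treatment criterion for interruption. From a baseline of 50% or more, the 40% limb of the stop row adds nothing, because any LVEF below 40% is then already a fall of more than 10 points. That limb acts only on the patients for whom the restart row says the opposite.

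What is at stake is dosing in patients with unrecovered left ventricular dysfunction, which Section 5.1.1.1.3 lists as an important identified risk of cobimetinib.

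**Working it through.** The plan gives no figure to reproduce; this is a logic check of the table cells. *Absolute decrease* is read as percentage points.

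**Notation.** B = baseline LVEF, L = post-break LVEF, N = the institution's lower limit of normal.

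**Conditions**
- Restart row (Table 5): B − L < 10
- Stop row (Table 5): L < 40 or B − L ≥ 10
- Entry (Section 4.1.2.2): B ≥ min(N, 50)

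**Where both rows apply.** The restart row rules out B − L ≥ 10, so both hold exactly when L < 40 and B − L < 10. Then B < L + 10 < 50. With B ≥ min(N, 50), this requires N < 50. If N is 50% or more, the overlap is empty.

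**Counting whole-percent pairs.** For a given B from 40 to 48, L runs from B − 9 to 39, which is 49 − B values. Summing from the lowest admissible B up to 48:

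| Site lower limit N | Pairs meeting both rows |
|---|---|
| 49% or higher | 0 |
| 48% | 1 (B = 48, L = 39) |
| 47% | 1 + 2 = 3 |
| 46% | 1 + 2 + 3 = 6 |
| 45% | 1 + 2 + 3 + 4 = 10 |
| 40% | 1 + 2 + … + 9 = 45 |

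If LVEF were recorded to 0.1 point, a lower limit of 49% would also admit some pairs (45 on that grid). A limit of 50% or more gives none at any resolution.

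**Example.** N = 45%, baseline 47% (eligible). On treatment, asymptomatic, LVEF is 38%: below 40%, so interrupt. After 2 weeks it is 39%. The fall is 47 − 39 = 8 points, so the restart row gives 40 mg. Because 39 < 40, the stop row gives permanent discontinuation. For contrast, with baseline 50% and a post-break value of 39% the fall is 11 points and only the stop row applies.

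**Occurrences.** The rows conflict at the first and second occurrence. At the third, both lead to discontinuation.

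**Gaps and the on-treatment rows.** No (B, L) pair escapes both post-break rows. On a whole-percent grid (B 40–80, L 10–80) the on-treatment rows have no overlap and no gap, so the defect is confined to the post-break rows.

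**Rough scale.** Section 5.1.1.1.3 reports "8.5% vs. 3.7%, respectively, of Grade 2 or 3 decreased LVEF", for cobimetinib plus vemurafenib against placebo plus vemurafenib.
- At full expansion: 250 × 0.085 = 21.25 patients with such a decrease.
- At initial enrolment: 6 × 20 + 12 = 132, and 132 × 0.085 = 11.2.
- Share with baseline under 50%: not in the documents; assumed 0 to 10%. This gives 0 to 2.1 patients at 250, and 0 to 1.1 at 132.

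These are upper figures, since the post-break value must also fall in the overlap.

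**The case against.** The overlap itself is not in dispute; its importance is.

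**The stop row is the natural reading.** Since its 40% limb affects only these low-baseline patients, treating the restart row as controlling would leave that limb with no function. A patient still below 40% also remains in the range that triggered the interruption. Table 4 (Section 5.1.3.1) points the same way: for intolerable Grade 2 or any Grade 3–4 toxicity, it restarts only after recovery to Grade 1 or better. This is sensible, and a cautious investigator would probably stop. But no sentence or footnote states the precedence, and Table 4 is more general than the LVEF rows it would have to override.

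**The harm is bounded.** An asymptomatic patient restarted at 39% would be rechecked at about 2 weeks, interrupted again if still below 40%, and stopped at the third occurrence. Section 4.6.1 requires stopping for any condition that may jeopardize safety. Section 5.2.3 makes symptomatic heart failure and Grade 3 or higher LVEF reduction reportable within 24 hours. The dose column is headed as a recommendation. All of this stands and keeps the consequence small. None of it settles the conflict: the rechecks come after the restart, and the other provisions leave the choice to judgment.

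**The affected set may be empty.** The documents give no site lower limits and no baseline LVEF distribution, so reachability at an actual site is unproven. That is right. However, about 20 centers take part globally (Section 9.4), the protocol sets no common lower limit, and the entry criterion expressly provides for limits below 50%.

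**Conclusion.** The table is wrong as written. After a break, an LVEF below 40% with a fall of less than 10 points meets both a restart row and a stop row, in the asymptomatic and the symptomatic block alike, at the first and second occurrence. The conflict arises only for baselines under 50%, hence only at sites whose lower limit of normal is under 50% (48% or lower if LVEF is recorded in whole percentages).

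The practical impact is low: probably rare, possibly nil, and at most about 2 patients on the assumed 0–10% share, before the further condition on the post-break value. The 8.5% rate is borrowed from a different combination. No effect on the efficacy endpoints or the safety summaries is claimed. It is nevertheless worth correcting, because the instructions are opposite, the risk is an identified cardiac one, and the remedy costs almost nothing.

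**What to change.** In both post-break restart cells, add the floor that the on-treatment rows already use:
- Asymptomatic block: *LVEF ≥ 40% and* "< 10% absolute decrease from baseline"
- Symptomatic block: *Asymptomatic, LVEF ≥ 40% and* "< 10% absolute decrease from baseline"

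Leave the stop rows unchanged. The restart condition becomes L ≥ 40 and B − L < 10, the exact complement of L < 40 or B − L ≥ 10, so every post-break value falls in one row only, for any lower limit of normal.

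The cost is two table cells, by amendment or clarification letter, with no added assessments. The downside is that a few patients with a low baseline would stop cobimetinib instead of restarting at a reduced dose.
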